11.0 APPENDIX

Appendix 1: Schedule of Activities

	Visit 1	Visit 2	Visit 3	Visit 4	Visit 5	Visit 6	Visit 7
	Screening and Baseline	Surgery and Discharge	7-14 Day F/U (+3 days)	30 Day F/U (± 7 days)	90 Day F/U (± 14 days)	180 Day F/U (± 30 days)	360 Day F/U (± 30 days)
Inclusion/Exclusion Review	X						
Informed Consent	X						
Patient Medical History	X						
Physical Exam	X						
Intraoperative Data ¹		X					
Clinical Assessments ²			X	X	X	X	X
MSTS Score and EORTC QLQ BM22	X		X	X	X	X	X
Pain Visual Analog Scale (VAS)	X		X	X	X	X	X
Radiographs of Fracture Area	X		X	X	X	X	X
Adverse Events		X	X	X	X	X	X
Concomitant/Pain Medications	X	X	X	X	X	X	X
Health Economic Assessment	X	X	X	X	X	X	X

¹ Including date of surgery, duration of surgery, impending fracture treatment used.

² Clinical assessments: standard fracture evaluations and other assessments, as appropriate, including but not limited to assessments for pain, return to pre-treatment mobility, range of motion, return to work, disability status, use of pain medication, and physical therapy prescription status.

Appendix 2: Classification of Visits

Timing of assessment (days relative to surgery ^a)	Visit	Visit Name to display for Analysis
Screening	Visit 1	Screening
Last assessment result collected prior to the surgery ^b	Baseline	Baseline
Surgery and Discharge (ie Day 1)	Visit 2	Surgery and Discharge
7-14 Day F/U (+3 days)	Visit 3	7-14 Day F/U
30 Day F/U (\pm 7 days)	Visit 4	30 Day F/U
90 Day F/U (\pm 14 days)	Visit 5	90 Day F/U
180 Day F/U (\pm 30 days)	Visit 6	180 Day F/U
360 Day F/U (\pm 30 days)	Visit 7	360 Day F/U

a. Day 1 is the day of surgery.

b. For subjects who have Screening and surgery visits on the same day, the values from the date of surgery will be considered for baseline. For range of motion tests, baseline values are defined as the measurements at 7-14 Day F/U visit.

Appendix 3: SAS Program for Conditional Power Calculation

```
*****
* CLIENT: ILLUMINOSS
* PROJECT: 14-03-PATHOLHUM-02
*****
* PROGRAM NAME: conditional_power_single_arm_three_timepoints
* PROGRAM LOCATION: c:\proj\proj\icon\illuminoss\anllib
* PROGARM PURPOSE: CALCULATES CONDITIONAL POWER GIVEN AN INTERIM OBSERVED DATASET.
*
* DETAILS: THE PRIMARY NULL AND ALTERNATIVE HYPOTHESES ARE:
* Ho: mean improvement in VAS at Day 90 <= 53.8
* Ha: mean improvement in VAS at Day 90 > 53.8
* WHERE VAS IS MEASURED AT BASELINE AND AT 3 POST-BASELINE VISITS
* (DAYS 7-4, 30 AND 90). THE NULL HYPOTHESIS WILL BE TESTED USING
* THE SAMPLE CHANGE FROM BASELINE VAS to at Day 90,
* AS CALCULATED BY AN MMRM MODEL (SEE BELOW FOR THE PROC MIXED CALL).
* AFTER the 37th PATIENTS who underwent surgery had Day 90 visit
* , AN INTERIM MMRM ANALYSIS ON CHANGE FROM BASELINE VAS to Day 90 WILL
* BE CARRIED OUT. THE PURPOSE OF THIS INTERIM ANALYSIS
* IS NOT TO STOP THE TRIAL FOR OVERWHELMING EFFICACY, BUT RATHER
* TO (A) POTENTIALLY STOP FOR FUTILITY AND (B) POTENTIALLY
* INCREASE THE SAMPLE SIZE IF THE MEAN VAS IMPROVEMENT FROM BASELINE
* to at Day 90 IS LARGE BUT NOT AS LARGE AS ANTICIPATED IN THE
* ORIGINAL SAMPLE SIZE CALCULATIONS. IN ORDER TO DO THIS,
* CONDITIONAL POWER (CP), CONDITIONED ON THE INTERIM OBSERVED
* DATA, NEEDS TO BE CALCULATED. THIS PROGRAM CALCULATES CP USING
* COMPUTER SIMULATIONS. 1000 SIMULATED POST-INTERIM DATASETS
* ARE CALCULATED UNDER THE EFFECT SIZES AND WITHIN-SUBJECT
*
CORRELATIONS
*
ESTIMATED FROM THE INTERIM OBSERVED DATA. EACH SIMULATED DATASET
WILL BE ADDED TO THE INTERIM OBSERVED DATA, AND THE MMRM-BASED
TESTING OF THE NULL HYPOTHESIS WILL BE CARRIED OUT. THE PROPORTION
OF SIMULATED DATASETS FOR WHICH THE NULL HYPOTHESIS IS REJECTED IS
THE SIMULATED CONDITIONAL POWER. NOTE: CONDITIONAL POWER IS
CALCULATED UNDER THE ASSUMPTION THAT THE CHARACTERISTICS (MEAN
AND STANDARD DEVIATION OF CHANGE FROM BASELINE VAS AT EACH VISIT,
WTIHIN-PATIENT CORRELATION OF VAS BETWEEN VISITS) ARE THE TRUE
POPULATION CHARACTERISTICS.
*
* SAS VERSION: 9.4
* AUTHOR: [name]
* DATE: 06Oct2015
* revision history: 7Mar2016-modified to test VAS change from baseline to Day 90 visit, per protocol amendment
v5.0;
*-----;
*/
/* FOR NOW, WE SIMULATE ONE "INTERIM" OBSERVED DATASET FROM THE POPULATION. */
/* NOTE THAT IN THE SIMULATIONS TO ESTIMATE CONDITIONAL POWER (CP) THAT */
/* WILL BE CARRIED OUT AT THE TRUE INTERIM ANALYSIS, THIS SIMULATED INTERIM */
```

```

/* OBSERVED DATA WILL BE REPLACED WITH THE ACTUAL INTERIM OBSERVED DATA      */
/* OF POST-BASELINE CHANGE FROM BASELINE VAS FOR EVALUABLE SUBJECTS.          */

/* TO SIMULATE THIS INTERIM OBSERVE DATASET, WE FIRST NEED TO ENTER          */
/* THE CHARACTERISTICS OF THE ASSUMED POPULATION IN A DATASET. SPECIFICALLY: */
/* THE FIRST ROW OF DATA IS THE ASSUMED MEAN OF BASELINE VAS AND OF THE       */
/* CHANGE FROM BASELINE VAS TO AT VISITS 1, 2 AND 3. THE SECOND ROW IS THE    */
/* ASSUMED S.D. OF VAS AT AND OF THE CHANGE FROM BASELINE VAS AT EACH OF       */
/* VISITS 1, 2 AND 3. THE THIRD ROW IS THE EVALUABLE SAMPLE SIZES              */
/* ANTICIPATED AT EACH VISIT FOR THE INTERIM ANALYSIS. ROWS 4-7 ARE           */
/* THE ASSUMED CORRELATION MATRIX (WITHIN-PATIENT CORRELATION OF CHANGE       */
/* FROM BASELINE VAS BETWEEN VISITS AND VS. BAESLINE VAS).                      */

data INTERIM_CHARACTERISTICS (type=corr);
    input _TYPE_ $ 1-4 _NAME_ $ 6-12 BASEVAS CHGVAS1 CHGVAS2 CHGVAS3;
cards;
MEAN      80    -38    -45    -58
STD       16     26     30     18
N         30     30     30     30
CORR BASEVAS 1.00 0.30 0.30 0.30
CORR CHGVAS1 0.30 1.00 0.40 0.16
CORR CHGVAS2 0.30 0.40 1.00 0.40
CORR CHGVAS3 0.30 0.16 0.40 1.00
run;

/* GENERATE A MULTIVARIATE NORMALLY DISTRIBUTED SAMPLE FROM THE POPULATION */
/* WITH THE ABOVE CHARACTERISTICS. THIS WILL TAKE THE PLACE OF               */
/* THE INTERIM OBSERVED SAMPLE FOR NOW . THIS DATASET WILL HAVE ONE          */
/* OBSERVATION PER PATIENT, WITH THE VARIABLES BASEVAS AND CHGVAS1-CHGVAS3, */
/* CONTAINING BASELINE VAS AND CHANGE FROM BASELINE VAS TO VISITS 1 - 3,      */
/* RESPECTIVELY.                                                               */

/* AGAIN, IN THE TRUE CP SIMULATIONS TO BE DONE AT THE INTERIM ANALYSIS,    */
/* THIS SIMULATED INTERIM OBSERVED DATA WILL BE REPLACED WITH THE ACTUAL      */
/* INTERIM OBSERVED DATA.                                                       */

proc simnormal data=INTERIM_CHARACTERISTICS numreal=30
    /* NUMREAL IS THE # OF ANTICIPATED OBSERVATIONS AT INTERIM, */
    seed=321248888 out=INTERIM_DATA;
    var baseVAS CHGVAS1-CHGVAS3;
run;

/* NOW RUN PROC MIXED ON THE INTERIM OBSERVED DATA, PRIMARILY TO CALCULATE   */
/* AN ESTIMATE OF THE CORRELATION MATRIX BETWEEN VISITS AND THE ESTIMATE     */
/* OF THE INTERIM OBSERVED MEAN AND STANDARD ERROR. THESE CHARACTERSISTICS   */
/* WILL BE LATER USED TO SIMULATE 1000 POST-INTERIM VAS DATASETS FROM A      */
/* POPULATION WITH THE SAME CHARACTERISTICS OF THE INTERIM OBSERVED DATA,    */
/* IN ORDER TO EVENTUALLY CALCULATED CP UNDER THE ASSUMPTION THAT THE        */
/* INTERIM DATASET CHARACTERISTICS ARE THE SAME CHARACTERISTICS AS THE       */
/* POPULATION.                                                               */

data INTERIM_DATA_STACKED;

```

```
set INTERIM_DATA;
subjid=rnum;
visit=1; CHGvas=CHGvas1; output;
visit=2; CHGvas=CHGvas2; output;
visit=3; CHGvas=CHGvas3; output;
keep subjid baseVAS visit CHGvas;
run;
/* THE RCORR OPTION BELOW YIELDS AN ESTIMATE OF THE CORRELATION MATRIX,      */
/* THE LSMEANS STATEMENT YIELDS AN ESTIMATE OF THE MEAN CHANGE FROM           */
/* BASELINE VAS AND ITS STANDARD ERROR AT EACH OF VISITS 1-3.                  */
proc mixed data=INTERIM_DATA_STACKED method=ml;
  class visit subjid;
  model CHGvas = visit baseVAS/ ddfm=kr;
  repeated visit / type=un subject=subjid r rcorr;
  lsmeans visit / /*diff adjust=GT2 adjdf=row*/;
run;
quit;
/* OBTAIN AN ESTIMATE OFF THE BASELINE MEAN VAS AND THE CORRELATION OF      */
/* BASELINE VAS WITH EACH CHANGE FROM BASELINE VAS.                            */
proc corr data=INTERIM_DATA;
  var baseVAS;
  with CHGvas1-CHGvas3;
run;

/* NOW TAKE THE OPERATIONAL CHARACTERISTICS ESTIMATED FROM ABOVE STATEMENTS, */
/* AND ASSUME THAT THESE CHARACTERISTICS DEFINE THE POPULATION FROM WHICH     */
/* THE POST-INTERIM SAMPLE IS TAKEN. WE WILL SIMULATE 1000 POST-INTERIM        */
/* SAMPLES FROM THIS POPULATION. FOR EACH SIMULATED SAMPLE, WE WILL           */
/* COMBINE IT WITH THE ABOVE INTERIM OBSERVED SAMPLE. WE WILL THEN           */
/* CALCULATE THE PROPORTION OF THESE 1000 COMBINED DATASETS FOR WHICH THE     */
/* NULL HYPOTHESIS OF THE STUDY IS REJECTED. THIS IS OUR CONDITIONAL          */
/* POWER (CP) UNDER THE ASSUMPTION THAT THE CHARACTERISTICS OF THE             */
/* INTERIM OBSERVED DATASET ARE THE TRUE CHARACTERISTICS OF THE POPULATION. */

/* TO START OUT, CREATE A DATASET CONTAINING THE CHARACTERISTICS OF THE        */
/* POPULATION. FOR THE DATASET BELOW:
/* THE FIRST ROW OF DATA IS THE INTERIM OBSERVED MEAN OF BASELINE VAS          */
/* (ESTIMATED FROM THE ABOVE PROC CORR) AND OF THE CHANGE FROM BASELINE VAS      */
/* TO VISITS 1 - 3 (ESTIMATED FROM THE LSMEANS STATEMENT OF THE ABOVE PROC      */
/* MIXED STATEMENT. THE SECOND ROW OF DATA IS THE INTERIM OBSERVED               */
/* STANDARD DEVIATION OF BASELINE VAS ESTIMATED FROM THE ABOVE PROC CORR)        */
/* AND OF THE CHANGE IN BASELINE VAS TO VISITS 1, 2 AND 3 (ESTIMATED             */
/* BY TAKING THE ESTIMATED STANDARD ERRORS FROM THE LSMEANS STATEMENT          */
/* OF THE ABOVE PROC MIXED AND MULTIPLYING THEM BY THE SQUARE ROOT               */
/* OF THE SAMPLE SIZE AT EACH VISIT). THE THIRD ROW ARE THE PLANNED EVALUABLE */
/* SAMPLE SIZES AT EACH VISIT POST-INTERIM. ROWS 4-7 ARE THE ESTIMATED          */
/* CORRELATION MATRIX FROM THE INTERIM OBSERVED DATA.                           */
/* data POST_INTERIM_CHARACTERISTICS (type=corr);
```

```

input _TYPE_ $ 1-4 _NAME_ $ 6-12 BASEVAS CHGVAS1 CHGVAS2 CHGVAS3;
cards;
MEAN      77.7 -40.9 -46.2 -60.4
STD       13.5 23.1 28.1 16.5
N         38   38   38   38
CORR BASEVAS 1.00 0.44 0.43 0.02
CORR CHGVAS1 0.44 1.00 0.20 0.26
CORR CHGVAS2 0.43 0.20 1.00 0.10
CORR CHGVAS3 0.02 0.26 0.10 1.00
run;

```

```

/* SIMULATE THE 1000 POST-INTERIM ANALYSIS DATASETS. EACH DATASET WILL      */
/* BE COMBINED WITH THE INTERIM OBSERVED DATASET IN ORDER TO CREATE 1000      */
/* COMPLETE SIMULATED CLINICAL TRIALS. FOR EACH TRIAL, A PROC MIXED      */
/* ANALYSIS WILL BE CARRIED OUT TO TEST THE STUDY'S NULL HYPOTHESIS.      */
/* THE PROPORTION OF SIMULATED DATASETS FOR WHICH THE NULL HYPOTHESIS IS      */
/* REJECTED IS THE SIMULATED CONDITIONAL POWER.                          */
/* */
%MACRO DOIT2;
data POST_INTERIM_CHARACTERISTICS(type=corr);
    %DO I=1 %TO 1000;
        simulation=&I;
        set POST_INTERIM_CHARACTERISTICS;
        OUTPUT;
    %END;
run;
%MEND DOIT2;
%DOIT2;
proc sort data=POST_INTERIM_CHARACTERISTICS;
    by simulation;
run;
/* SIMULATE A MULTIVARIATE NORMAL DISTRIBUTION FOR BASELINE AND CHANGE FROM      */
/* BASELINE VAS TO VISITS 1 - 3 UNDER THE ABOVE CHARACTERISTICS FOR EACH SIMULATION.*/
proc simnormal data=POST_INTERIM_CHARACTERISTICS numreal=38 seed=315893282 out=POST_INTERIM_DATA;
    by simulation;
    var baseVAS CHGvas1-CHGvas3;
run;
data POST_INTERIM_DATA;
    set POST_INTERIM_DATA;
    subjid=rnum+100000; /* MAKE SURE SUBJIDSFOR POST-INTERIM DATA ARE NOT      */
                        /* THE SAME AS SUBJECT IDS FROM INTERIM DATA.      */
    drop rnum;
run;
/* COMBINE EACH SIMULATED DATASET WITH THE INTERIM OBSERVED DATASET.      */
/* THIS IS DONE BY FIRST MAKING 1000 COPIES OF THE INTERIM OBSERVED DATA,      */
/* AND THEN ADDING ONE COPY TO EACH OF THE 1000 SIMULATED POST-INTERIM      */
/* DATASETS.      */
%MACRO DOIT3;
data INTERIM_DATA;
    %DO I=1 %TO 1000;

```

```
simulation=&I;
set INTERIM_DATA;
subjid=rnum;
OUTPUT;
%END;
drop rnum;
run;
%MEND DOIT3;
%DOIT3;

data FINAL;
    set INTERIM_DATA POST_INTERIM_DATA;
run;
proc sort data=FINAL NODUPKEY;
    by simulation subjid;
run;

/* ARRANGE THE DATA SO THAT PROC MIXED CAN BE CARRIED OUT FOR EACH SIMULATED */
/* DATASET. */
data FINAL_STACKED;
    set FINAL;
    visit=1; CHGvas=CHGvas1; output;
    visit=2; CHGvas=CHGvas2; output;
    visit=3; CHGvas=CHGvas3; output;
    keep simulation subjid baseVAS visit CHGvas;
run;

ods select none;
/* THE LSMESTIMATE STATEMENT BELOW CONDUCTS A TEST OF THE ABOVE NULL */
/* HYPOTHESIS OF INTEREST. */
proc mixed data=FINAL_STACKED method=ml;
    by simulation;
    class visit subjid;
    model CHGvas = visit baseVAS/ ddfm=kr;
    repeated visit / type=un subject=subjid r rcorr;
    lsmeans visit / /*diff adjust=GT2 adjdf=row*/;
    lsmeans estimate visit 0 0 1/lower testvalue=-53.8;
    ods output lsmestimates=lsmestimates;
run;
quit;
ods select all;

/* DETERMINE THE PROPORTION OF SIMULATIONS FOR WHICH THE NULL HYPOTHESIS */
/* IS REJECTED. THIS IS THE CONDITIONAL POWER. */
data FinalResult;
    set lsmestimates;if probt<=0.05 then reject=1;
    else reject=0;
run;
```

```
proc freq data=FinalResult;  
    table reject;  
run;
```

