3.5 Sample Size Justification

Approximately 80 subjects will be enrolled into this study. The following text will give sample size justification details.

VAS pain improvement: The primary endpoint is change in VAS from baseline to Day 90. All patients will be included in the primary analysis of this endpoint through the use of a mixed model repeated measures (MMRM) model assuming an unstructured covariance matrix. To be conservative, statistical power is evaluated on the basis of a single-sample t-test with a 1-sided alpha=0.05 based on the change at Day 90. The null and alternative hypotheses of interest are:

$$H_0: \text{mean improvement in VAS at Day 90} \leq 53.8$$

$$H_a: \text{mean improvement in VAS at Day 90} > 53.8$$

Based on the historical control data in protocol Section 6.3, an estimate of the standard deviation of the primary endpoint is 13.3. Under the assumption this is the true standard deviation, under the assumption the true mean improvement from baseline VAS at Day 90 is 58, then 68 evaluable patients yields over 80% power to reject the null hypothesis in favor of the alternative. In order to account for 15% premature withdrawal rate, a total of 80 patients will be enrolled. Note that the assumption of 58 for the true mean improvement from baseline VAS at 90 days may be conservative given the historical control data in protocol Section 6.3 (where the overall mean change, or reference value, was estimated to be approximately 67, over a shorter period than 90 days).

MSTS improvement: The second primary endpoint, to be tested if the above null hypothesis for improvement in VAS is rejected, is change in MSTS from baseline at Day 90; this will be analyzed a similar MMRM manner as the primary endpoint above. The null and alternative hypotheses of interest for this endpoint are:

$$H_0: \text{mean improvement in MSTS at Day 90} \leq 23.7$$

$$H_a: \text{mean improvement in MSTS at Day 90} > 23.7$$

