At the interim stage, the conditional power for rejecting the above null VAS hypothesis by the time of the final analysis (a planned 68 evaluable patients) will be calculated, conditioned on the interim observed data. Patient is evaluable if he/she has VAS measurement at both baseline and Day 90 visit. The conditional power will be calculated using 1000 Monte Carlo simulations via a SAS program (see the appendix 3 for the SAS program, embedded with comments describing the program). The simulation of conditional power requires an assumption of (a) the true mean change in baseline VAS at each visit; (b) the true standard deviation of the change from baseline VAS at each visit; and (c) the true within-patient correlation of VAS. These values will be estimated from the interim observed sample, and these estimated values will be used as the assumption of the true values in the conditional power simulation. Once the interim observed sample is obtained, 1000 post-interim samples will be generated assuming that 38 (i.e. 68-30) evaluable patients will be enrolled post-interim (since, again, the total evaluable sample size is 68 patients, and assume that 30 evaluable patients among the first 37 patients are in the interim analysis, actual number of evaluable patients in interim analysis will be determined with actual interim data), and each of these simulated samples will be added to the one interim observed sample to create 1000 simulated complete-study datasets of 68 evaluable patients. On each simulated dataset, the following SAS statements will be used to test the above null hypothesis:

```
proc mixed method=ml;  
  by simulation;  
  class visit subjid;  
  model CHGvas = visit baseVAS/ ddfm=kr;  
  repeated visit / type=un subject=subjid r rcorr;  
  lsmeans visit / ;  
  lsmeans estimate visit 0 0 1/lower testvalue=-53.8;  
run;
```

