where the input dataset has 3 records per patient (one record per visit) where the variable CHGVAS contains the change from baseline VAS score for that patient-visit, VISIT is a categorical variable which identifies the Day 7-14, Day 30, and Day 90 assessments, baseVAS is the baseline VAS, and SUBJID is the subject ID. The interim estimated mean change from baseline VAS at Day 90, the test-statistic, and the corresponding one-sided p-value for the above-mentioned null hypothesis are obtained from the “LSMESTIMATE” statement. The proportion of simulated datasets for which the one-sided p-value is below 0.05 is the simulated conditional power. Note that the above PROC MIXED statements will be used for the final analysis once all data are collected.

If the above simulated conditional power is $\geq 80\%$ when the final evaluable sample size for the simulated samples is equal to the pre-planned number of evaluable subjects (68), the study will continue as is. If the simulated conditional power is between 10% and 50%, the study will also continue as is. If the simulated conditional power is $<10\%$, the study may be stopped for futility. If, however, the conditional power is between 50% and 80%, then the evaluable sample size

increase required to achieve 80% simulated conditional power will be calculated using the Chen-DeMets-Lan (CDL) approach⁸. Specifically, if the simulated conditional power is between 50% and 80% with a total sample of size 68 evaluable patients, then the evaluable sample size increase (from beyond the pre-planned 68) required to achieve a simulated conditional power of 80% will be determined by plugging in increasing values of post-interim sample sizes into the conditional power program, and determining the sample size at which the conditional power achieves 80%.

Under the above CDL approach, an “alpha-penalty” does not need to be made for any sample size increase in this setting as long as the maximum sample size increase required to maintain 80% power is below the bound $100*R\%$ of the original sample size, where R is calculated as follows:

$$\sqrt{1+R}(\sqrt{1+R}-1)/\sqrt{1+R-s} = t_{0.80,df}/t_{0.95,df}$$

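### The conditional-power program enters a baseline-adjusted SD as if it were the SD of change, so the interim sample-size increase can be mis-sized (about 10 evaluable patients too few at the program's first illustrative row)

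*SAP*

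**What the plan says.** SAP Section 8.0 lists what the simulation must assume, including "b) the true standard deviation of the change from baseline VAS at each visit", and says that these values are estimated from the interim sample. If conditional power at 68 evaluable patients lies between 50% and 80%, the same program sets the new sample size by trying larger post-interim samples and "determining the sample size at which the conditional power achieves 80" percent.

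Appendix 3 gives the recipe for the post-interim population:

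- **SDs of change:** obtained "BY TAKING THE ESTIMATED STANDARD ERRORS FROM THE LSMEANS STATEMENT" and multiplying by the square root of the sample size. The model is "model CHGvas = visit baseVAS/ ddfm=kr", fitted with method=ml.
- **Between-visit correlations:** from the same model; the comment reads "THE RCORR OPTION BELOW YIELDS AN ESTIMATE OF THE CORRELATION MATRIX".
- **Baseline mean and SD, and the correlations of baseline with change:** from PROC CORR on the raw interim data.

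All of these go into one PROC SIMNORMAL matrix. Each simulated trial is then analysed with baseline VAS in the model again. The comments describe the matrix as holding the characteristics of the interim data.

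**The concern.** PROC SIMNORMAL needs the marginal SDs and correlations of baseline and the three changes. The recipe supplies residual SDs and residual between-visit correlations beside marginal correlations with baseline. These do not belong to one distribution, and no later step restores the unadjusted SD.

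The part of the variance explained by baseline is taken out before simulation and again in the analysis. Where baseline and Day 90 change are clearly correlated, the simulated Day 90 means vary too little and their standard errors come out too small. In the promising zone both raise conditional power.

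The stake is the interim decision. In the 50-80% zone this program alone sets the increase, so the trial can be enlarged by too few patients, or by too many if the bias runs the other way. Near a zone limit the decision itself can change. The final test and its type I error are not touched.

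**Working it through.** **The plan's own figures reproduce.** From SAP Section 3.5 (null 53.8, true mean 58, SD 13.3, n = 68, one-sided 0.05), the noncentrality is 4.2/(13.3/√68) = 2.60 and the power is 82.5%, against a stated value of over 80%. The bound in Section 8.0 gives R = 1.085 and 141.8 evaluable patients, against 1.08 and 142. The SAP states no conditional power for its illustrative rows.

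**Inputs.** The INTERIM_CHARACTERISTICS row of Appendix 3 has a baseline SD of 16, a Day 90 mean change of -58 with SD 18, and "CORR BASEVAS 1.00 0.30 0.30 0.30". There are 30 interim patients and 38 to come (Section 8.0).

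**SD that the program enters.** With complete data, the LSMEANS standard error times √n is the ML residual SD. The model fits one baseline slope for all visits, here 0.39. The covariance of baseline and Day 90 change is 0.30 × 16 × 18 = 86.4. The Day 90 residual variance is

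18² - 2(0.39)(86.4) + 0.39²(16²) = 324 - 67.4 + 38.9 = 295.5.

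The ML divisor multiplies this by 29/30, giving 285.7. The SD entered is √285.7 = 16.9, not 18.

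**Simulation.** The program was re-coded with 30 interim patients having exactly the stated means, SDs and correlations. Data were complete, and N-1 degrees of freedom replaced Kenward-Roger. Conditional power at mean improvement 58 (20,000 replicates):

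| Evaluable N | Consistent inputs | Program |
|---|---|---|
| 68 | 68.1% | 71.9% |
| 84 | 76.0% | 79.6% |
| 86 | 76.9% | 80.5% |
| 94 | 79.7% | 83.1% |
| 96 | 80.2% | 83.9% |

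By interpolation the program stops at about 85 (increase 17) and consistent inputs need about 95 (increase 27). At 85, conditional power with consistent inputs is about (76.0 + 76.9)/2 = 76.5%. A run with 60,000 replicates put the two sizes at 84.3 and 94.0, a gap of 9.7.

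**Closed-form check, without the ML divisor.** Let s be the SD of change for the n₂ new patients, w their residual SD, and 17.17 = 18√(1 - 0.30²) the interim residual SD. Then

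CP ≈ Φ{[4.2 - t√(v/N)] / (s√n₂/N)}, with v = (30 × 17.17² + n₂w²)/N.

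At N = 68, n₂ = 38 and t = 1.668:

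- Consistent (s = 18, w = 17.17): (4.2 - 3.473)/1.632 = 0.446, so 67%.
- Program (s = 17.17, w = 17.17√0.91 = 16.38): (4.2 - 3.385)/1.556 = 0.524, so 70%.

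The sample sizes for 80% are 96 and 89, a gap of 7.

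**What drives the gap.** In the 60,000-replicate run, correcting only the SD moved the program's 84.3 to 94.0. Correcting only the between-visit correlations left it at 84.3. With an n-1 divisor in the residual SD it was 86.7. So about 7 of the 10 patients come from the baseline adjustment of the SD and 2 to 3 from the ML divisor.

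**Zone limits and direction** (40,000 replicates, N = 68):

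| Baseline correlations | Day 90 SD: true, entered | Mean improvement | Consistent | Program |
|---|---|---|---|---|
| 0.30 at all visits | 18, 16.9 | 57.2 | 49.6% | 52.4% |
| | | 58.5 | 77.9% | 81.4% |
| 0.44/0.43/0.02, other values from first row | 18, 18.24 | 57.5 | 50.6% | 49.4% |
| | | 58.9 | 80.5% | 79.2% |
| Whole second row as raw moments (assumption) | 16.5, 17.1 | 57.2 | 49.2% | 47.0% |
| | | 58.6 | 81.3% | 78.9% |
| -0.5 at all visits (assumption) | 18, 15.4 | 56.9 | 49.7% | 56.0% |
| | | 58.0 | 74.4% | 82.5% |

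The reversal comes from the common slope. In the second row, "CORR BASEVAS 1.00 0.44 0.43 0.02", the early visits pull the slope to 0.429 although Day 90 is almost uncorrelated with baseline. The Day 90 residual variance is 16.5² - 2(0.429)(0.02 × 13.5 × 16.5) + 0.429²(13.5²) = 272.3 - 3.8 + 33.5 = 302.0. Times 29/30 this gives an SD of 17.1, above the raw 16.5.

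**The case against.** **The adjusted SD suits an adjusted test.** That would hold if change were simulated around the fitted baseline slope with the residual covariance. The program instead enters the raw baseline correlations too, so the baseline variance is removed twice. This defence fails.

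**The row is a placeholder.** The first row stands in for real data, and its values describe a population, not an observed sample. At the second row's own mean of 60.4, conditional power is 97-98% either way and no increase arises. With the design SD of 13.3, mean 58 and correlations of 0.30 it is 92% against 94%, and both mean continuing unchanged. With SD 18 and correlations of 0.10 the gap is about 0.4 points. All of this stands: the 10 patients belong to one row and are not a forecast.

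**The practical effect is small.** At correlations of 0.30 the decision changes only for interim means of about 57.1-57.2 and 58.4-58.6. The standard error of the interim mean is 18/√30 = 3.3 mm, so these bands are narrow. The SAP permits an increase and does not require one. This stands for the zone decision. It does not cover the size of the increase, which is affected throughout the 50-80% zone. Simulation noise does not hide it: with 1000 runs the standard error near 80% is √(0.8 × 0.2/1000) = 1.3 points. At about 0.45 points per patient that is roughly 3 patients, against a shortfall of 10.

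**RCORR is not a driver.** This stands for complete data. The SD carries the effect.

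**Conclusion.** The concern holds. The program's inputs are not the SDs of change that Section 8.0 calls for, nor the characteristics of the interim data that its comments promise.

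At the first illustrative row, conditional power is overstated by about 4 points and the increase is about 10 evaluable patients too small. The roughly 95 patients needed lie well below the SAP's limit of 142, so the plan would have allowed them without an alpha penalty.

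The size and sign depend on the data. Of 150 random interim samples drawn from that row's population, 22 had a consistent conditional power of 50-80%; in these the program was on average 4 points too high, with a range of -2 to +9.

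The figures assume complete visits, 30 interim patients and N-1 degrees of freedom. The SAS seeds were not rerun, and missing early visits were not examined. The matter is worth correcting before the interim analysis but does not threaten the final inference.

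**What to change.** Fill the post-interim matrix with unadjusted moments: run PROC CORR on BASEVAS and CHGVAS1-CHGVAS3 together, and take all four SDs and the full 4×4 correlation matrix from it. If visits are missing, use an unstructured fit with baseline stacked as a fourth response, by REML so that the ML divisor does not return.

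Alternatively, simulate change given baseline from the fitted slope and residual covariance, again without the ML divisor. Either route is coherent; LSMEANS standard errors times √n and RCORR should not be combined with raw baseline correlations.

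The Appendix 3 comments on the source of the SDs and correlations need the same edit. The input list in Section 8.0 can stand. The cost is a few lines of code and a few minutes of computing. No new data are needed, and the thresholds, alpha and final analysis do not change.
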